## 7.2 Clinical Laboratory Parameters

Laboratory results will be summarized using Système International (SI) units, as appropriate.

Safety Assessments (Laboratory Measurements), the actual value and the change from baseline to each post-baseline visit and to the end of treatment (defined as the last on-treatment value) will be summarized by visit, treatment group and overall using descriptive statistics and changes from baseline to each post-baseline visit and to end of treatment will be reported using shift tables. Percentages will be based on the number of subjects with both non-missing baseline and relevant post-baseline results.

Blood and urine samples for clinical chemistry and hematology will be collected at the timepoints described in APPENDIX 1. PROTOCOL SCHEDULE OF ASSESSMENTS AND PROCEDURES. Laboratory parameters that will be assessed will include, but not be limited to:

Clinical laboratories to be assessed will be as below:

- Complete Blood Count with differential: must include hemoglobin, hematocrit, platelet count, total white blood cell counts with five-part differential count, and total red blood cell count
- Comprehensive Metabolic Panel: must include serum creatinine, blood urea nitrogen, glucose, total protein, albumin, total bilirubin, alanine aminotransferase, aspartate aminotransferase, alkaline phosphatase, electrolytes (sodium, potassium, chloride), calcium, bicarbonate, and creatine phosphokinase.

- Coagulation Panel: partial thromboplastin time (PTT) and prothrombin time international normalized ratio (INR).

Clinical laboratory assessments taken from blood sampling, such as hematology, chemistry, and coagulation, will be summarized and listed for the Safety Population.

### 7.3 Other Analyses

Not Applicable

## 8 CHANGES IN THE STATISTICAL METHODS FROM THOSE STATED IN THE PROTOCOL

Not Applicable

## 9 DEFINITIONS AND CONVENTIONS FOR DATA HANDLING

### 9.1 Algorithms for Efficacy Parameters

The following procedures will be used to determine the PFT and total scores for the efficacy parameters PedsQL Generic core scales, GI, and NMM.

#### 9.1.1 Pulmonary Function Test

Three sets of observations are measured for each variable in PFT. The “best” of the 3 values to be flagged according to the following procedure:

**STEP 1:** Order the 3 values to low, middle, high

**STEP2:** Calculate the % difference between the middle and the high value.

$$\% \text{difference} = (\text{high} - \text{middle}) / \text{high}$$

#### STEP3:

if the %difference is  $\leq 10\%$  then flag the high value as the best value

If the %difference is  $> 10\%$  then flag the middle value as the best value

The **low** value will never be used.

### **9.1.2 Quantitative Muscle Testing (QMT)**

QMT is measured by strength measured in pounds for flexion and extension of both elbows and knees. QMT is reported as an Arm QMT Value, Leg QMT Value, and Total QMT Value.

**STEP 1:** Calculate Arm QMT Value: left elbow flexion + left elbow extension + right elbow flexion + right elbow extension

**STEP 2:** Calculate Leg QMT Value: left knee flexion + left knee extension + right knee flexion + right knee extension

**STEP 3:** Calculate Total QMT Score: Arm QMT Value + Leg QMT Value

**STEP 4:** Calculate indexed Arm QMT Value, Leg QMT Value, and Total QMT Value as follows:

**For subjects  $\leq$ 20 years of age:**

Indexed Arm QMT = Arm QMT Value/age (lbs/years)

Indexed Leg QMT = Leg QMT Value/age (lbs/years)

Indexed Total QMT = Total QMT/age (lbs/years)

**For subjects greater than 20 years, QMT values will be divided by 20.**

### **9.1.3 Pediatric Quality of Life Inventory (PedsQL) 4.0 Generic Core Scales**

The Child, Young Adult, Adult, and Parent Reports of the **PedsQL™ 4.0 Generic Core Scales** for:

- Young Children (ages 5-7)
- Children (ages 8-12)
- Teens (ages 13-17)
- Young adults (ages 18-25)
- Adults (ages over 26)

are composed of 23 items comprising 4 dimensions.

Total Score were designed to measure the core dimensions of health as delineated by the World Health Organization, as well as role (school) functioning.

**DESCRIPTION OF THE QUESTIONNAIRE:**

Dimensions	Number of Items	Cluster of Items	Reversed scoring	Direction of Dimensions
Physical Functioning	8	1-8	1-8	
Emotional Functioning	5	1-5	1-5	
Social Functioning	5	1-5	1-5	
School Functioning	5	1-5	1-5	Higher scores = Better HRQOL

**SCORING OF DIMENSIONS**

Item Scaling	CHILD and PARENT Reports for Young Children (ages 5-7), Children (ages 8-12), and Teens (ages 13-18)	Young adult, adult and Parent Reports for young Adults (ages 18-25) and Adults (ages over 26)
	5-point Likert scale from: 0 (Never) to 4 (Almost always) 3-point Likert scale from: 0 (Not at all), 2 (Sometimes) and 4 (A lot) for the Young Child (ages 5-7) child report	5-point Likert scale from: 0 (Never) to 4 (Almost always)
Weighting of Items	No	
Extension of the Scoring Scale	Scores are transformed on a scale from 0 to 100	
Scoring Procedure	
Step 1: Transform Score
 
Items are reverse scored and linearly transformed to a 0-100 scale as follows: 0=100, 1=75, 2=50, 3=25, 4=0
 
Step 2: Calculate Scores by Dimensions:
	

	

• If more than 50% of the items in the scale are missing, the scale scores should not be computed

• Mean score = Sum of the items over the number of items answered

 
Psychosocial Health Summary Score = Sum of the items over the number of items answered in the Emotional, Social, and School Functioning Scales
 
Physical Health Summary Score = Physical Functioning Scale Score
 
Total Score: Sum of all the items over the number of items answered on all the Scales

Interpretation and Analysis of Missing Data	If more than 50% of the items in the scale are missing, the Scale Scores should not be computed.  If 50% or more items are completed: Impute the mean of the completed items in a scale.

#### 9.1.4 PEDsQL™ 3.0 Gastrointestinal Symptom Module Total Score

The Child, Young Adult, Adult, and Parent Reports of the PedsQL™ 3.0 Gastrointestinal Symptoms Module for:

- Young Children (ages 5-7)
- Children (ages 8-12)
- Teens (ages 13-18)
- Young adults (ages 18-25)
- Adults (ages over 26)

are composed of 74 items comprising 14 dimensions and sum of all 74 non-missing transformed variables divided by the questions answered(non-missing).

**DESCRIPTION OF THE GASTROINTESTINAL SYMPTOMS MODULE:**

Dimensions	Number of Items	Cluster of Items	Reversed Scoring	Direction of Dimensions
Stomach Pain and Hurt	6	1-6	1-6	
Stomach Discomfort When Eating	5	1-5	1-5	
Food and Drink Limits	6	1-6	1-6	
Trouble Swallowing	3	1-3	1-3	
Heart Burn and Reflux	4	1-4	1-4	
Nausea and Vomiting	4	1-4	1-4	
Gas and Bloating	7	1-7	1-7	
Constipation	14	1-14	1-14	Higher scores = Better HRQOL and fewer problems or symptoms
Blood in Poop (Bowel Movement)	2	1-2	1-2	
Diarrhea	7	1-7	1-7	
Worry About Going Poop (Bowel Movements)	5	1-5	1-5	
Worry About Stomach Aches	2	1-2	1-2	
Medicines	4	1-4	1-4	
Communication	5	1-5	1-5	

**SCORING OF DIMENSIONS**

Item Scaling	CHILD and PARENT Reports for Young Children (ages 5-7)	CHILD, YOUNG ADULT, ADULT, and PARENT Reports for Children (ages 8-12), Teens (ages 13-18) Young Adults (ages 18-25), and Adults (ages over 26)
	5-point Likert scale from: 0 (Never) to 4 (Almost always) 3-point Likert scale from: 0 (Not at all), 2 (Sometimes) and 4 (A lot) for the Young Child (ages 5-7) child report	5-point Likert scale from: 0 (Never) to 4 (Almost always)
Weighting of Items	No	

Extension of the Scoring Scale	Scores are transformed on a scale from 0 to 100
Scoring Procedure	
Step 1: Transform Score
 
Items are reverse scored and linearly transformed to a 0-100 scale as follows: 0=100, 1=75, 2=50, 3=25, 4=0
 
Step 2: Calculate Scores by Dimensions:
 

• If more than 50% of the items in the scale are missing, the scale scores should not be computed

• Mean score = Sum of the items over the number of items answered

 
Symptoms Total Scales Score: Sum of the items over the number of items answered in the 10 Symptoms Scales
 
Total Score: Sum of all the items over the number of items answered on all the Scales

Interpretation and Analysis of Missing Data	If more than 50% of the items in the scale are missing, the Scale Scores should not be computed.  If 50% or more items are completed: Impute the mean of the completed items in a scale.

### 9.1.5 PEDsQL™ 3.0 Neuromuscular Module Total Score

The Child, Young Adult, Adult, and Parent Reports of the PedsQL™ 3.0 Neuromuscular Module for:

- Young Children (ages 5-7)
- Children (ages 8-12)
- Teens (ages 13-18)
- Young adults (ages 18-25)
- Adults (ages over 26)

are composed of 25 items comprising 3 dimensions, whereas the Child Report for young children (ages 5-7) consists of only 17 items and comprising 1 dimension. sum of all 25 non-missing transformed variables (parent and child reports) and 17 non-missing transformed variables (child report) divided by the non-missing questions.

### THE CHILD DESCRIPTION OF THE NEUROMUSCULAR MODULE:

Dimensions	Number of Items	Cluster of Items	Reversed Scoring	Direction of Dimensions
About My Neuromuscular Disease	17	1-17	1-17	Higher scores = Better HRQOL and fewer problems or symptoms

### THE CHILD AND PARENT DESCRIPTION OF THE NEUROMUSCULAR MODULE:

Dimensions	Number of Items	Cluster of Items	Reversed Scoring	Direction of Dimensions
About Neuromuscular Disease	17	1-17	1-17	Higher scores = Better HRQOL and fewer problems or symptoms
Communication	3	1-3	1-3	
About Our Family Resources	5	1-5	1-5	

### SCORING OF DIMENSIONS

Item Scaling	CHILD Reports for Young Children (ages 5-7)	CHILD, YOUNG ADULT, ADULT, and PARENT Reports for Young Children (ages 5-7), Children (ages 8-12), Teens (ages 13-18), Young Adults (ages 18-25), and Adults (ages over 26)
	3-point Likert scale: 0 (Not at all), 2 (Sometimes), 4 (A lot)	5-point Likert scale from: 0 (Never) to 4 (Almost always)
Weighting of Items	No	

Extension of the Scoring Scale	Scores are transformed on a scale from 0 to 100
Scoring Procedure	
Step 1: Transform Score
 
Items are reverse scored and linearly transformed to a 0-100 scale as follows: 0=100, 1=75, 2=50, 3=25, 4=0
 
Step 2: Calculate Scores by Dimensions:
 

• If more than 50% of the items in the scale are missing, the scale scores should not be computed

• Mean score = Sum of the items over the number of items answered

 
Total Score: Sum of all the items over the number of items answered on all the Scales

Interpretation and Analysis of Missing Data	If more than 50% of the items in the scale are missing, the Scale Scores should not be computed.  If 50% or more items are completed: Impute the mean of the completed items in a scale.

## 9.2 Interobserver Variability

The level of agreement or consistency between different observers (or reviewers) when they evaluate, measure, or categorize the same test on the same subjects is referred to as interobserver variability, also known as interrater reliability or interrater variability.

## 10 DEFINITIONS AND CONVENTIONS FOR DATA HANDLING

The rules for programming derivations and dataset specifications are provided in separate documents.

## 11 STATISTICAL SOFTWARE

All statistical analyses will be performed by using SAS Version 9.4 or later.

## 12 MOCK TABLE, LISTING AND GRAPHS (TLGS)

The study TLG shells will be provided in a separate document, which will show the content and format of all tables, listings, and graphs in detail.

## 14 APPENDIX

### 14.1 APPENDIX 1. PROTOCOL SCHEDULE OF ASSESSMENTS AND PROCEDURES

	Screening Period		Treatment Period						Opt Ext	
	Visit(s)		Visit e	Phone Call/At-home	Phone Call	At-home	Visit e	Visit e	Phone Call/At-home	Visit e
	Week -12 to Week 0	Week -2 to Week 0	Day 0	Week 1 (± 2 days) (At home)	Month 1 (± 2 days) Month 3,5,7,9,11 (± 7 days)	Month 3 & 9 (At home)	Month 6 (± 7 days)	Month 12 (± 7 days)	Month 15, 18 & 21 (± 7 days)	Month 24 (± 7 days)
Informed Consent/Accent	X									
Medical/Surgical History, Demography	X									
Screening CMR or ECHO	X a									
Cystatin C		X								
Research CMR			X a				X	X		X
Physical Exam with vital signs		X	X b				X	X		X
Pulmonary Function Test			X				X	X		X
ECG, QMT & Actigraphy			X				X	X		X
PROs: PedsQL, GI & NMM			X			X	X	X	X d	X
CBC, CMP & Coagulation		X	X b				X	X		X
PK Blood Sampling			X c	X c						
Urine & blood for biomarkers			X				X	X		X
Review subject diary			X				X	X		X
Dispense IMP			X				X			
IMP Daily Dosing			I-----Continual Once Daily Dosing-----I							
Record Concomitant Medications			I-----Continual-----I							
AE/SAE Recording (if any)			I-----Continual-----I							

a -If screening CMR follows study-specific CMR protocol and was performed within 12 weeks of Baseline visit, Baseline CMR does not need to be repeated.

b - Screening Physical Exam, Complete blood count (CBC), Comprehensive metabolic panel (CMP) & Coagulation within 2 weeks of Baseline Visit need not be repeated.

c - PK blood sampling on Day 0: pre-dose, 30, 60 (±5) minutes; and 4, 8 and 24 hours (all ± 30 minutes) post dose. Day 7 (by subject at home): pre-dose and 30, (±5) minutes post-dose

d - Quality of life questionnaires are to be completed at home at Month 18 only. Safety phone calls are completed at Months 15, 18 and 21.

e - The site may split on-site study visits on Day 0, Month 6, Month 12, and Month 24 into two visits no more than 7 calendar days apart provided that each of the visit days remain within the protocol established window for the on-site Study Visits.

## 14.2 APPENDIX 2: Partial Date Recovery

Missing partial dates for prior/concomitant medications, and adverse events will be recovered with the following rules.

- If Start date is partial:
  - Missing day only
    - If the month and year are the same as the year and month of the first study treatment date, then the first dosing date will be assigned to the missing field.
    - If the partial date (year and month) is prior to the first study treatment date (year and month), then the last day of the month will be assigned to the missing field.
    - If the partial date (year and months) is after the first study treatment date (year and month), then the first day of the month will be assigned to the missing field.
  - Missing month only
    - The day will be treated as missing and both month and day will be imputed according to the imputation's rules for missing day and month.
  - Missing day and month
    - If the year is the same as the year of the first dosing date, then the first dosing date will be assigned to the missing field.
    - If the year is prior to the year of the first dosing date, then December 31 will be assigned to the missing field.
    - If the year is after the year of the first dosing date, then January 1st will be assigned to the missing field.
  - Missing year
    - No Imputation will be done.
    - If the stop date is non-missing and the imputed start date is after the stop date, the start date will be imputed by stop date.
- If End Date is partial:
  - Missing day only

- If the month and year are the same as the year and month of the last study treatment date, then the last dosing date will be assigned to the missing field.
- If the partial date (year and month) is prior to the last study treatment date (year and month), then the last day of the month will be assigned to the missing field.
- If the partial date (year and months) is after the last study treatment date (year and month), then the first day of the month will be assigned to the missing field.

- Missing month only

- The day will be treated as missing and both month and day will be imputed according to the imputation's rules for missing day and month.

- Missing day and month

- If the year is the same as the year of the last dosing date, then the last dosing date will be assigned to the missing field.
- If the year is prior to the year of the last dosing date, then December 31 will be assigned to the missing field.
- If the year is after the year of the last dosing date, then January 1st will be assigned to the missing field.

- Missing year

- No Imputation will be done.
- If the start date is non-missing and the imputed stop date is before the start date, the stop date will be imputed by start date.

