## **3.7 Study Period Definition**

The following definitions for the study periods are as follows: Double-blind period for efficacy or safety endpoints is defined as the time from randomization or first dose date, respectively, to:

- the last dose of double-blind study drug if the subject continues to the OL period or,
- the last study visit if the subject does not continue to the OL period.

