## **3.8 Open-Label Period**

Open-label period is defined as the time from the first dose of open-label study drug to the last study visit if the subject is enrolled into open-label extension period of the study.

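### Partial AE start dates are imputed against the first study dose only, so a partially dated open-label AE from the switch month or year is dated into the double-blind period

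*SAP*

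**What the plan says.** SAP 14.2 applies one set of rules to adverse events and to medications: "Missing partial dates for prior/concomitant medications, and adverse events will be recovered with the following rules". Every start date is compared with the first study treatment date:

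- Day missing, later month: "If the partial date (year and months) is after the first study treatment date (year and month), then the first day of the month" is used.
- Day and month missing, same year as first dose: "If the year is the same as the year of the first dosing date, then the first dosing date will be assigned to the missing" part.
- Day and month missing, later year: "If the year is after the year of the first dosing date, then January 1st will be assigned to the missing field".
- The only other adjustment to a partial start is the stop-date cap: "If the stop date is non-missing and the imputed start date is after the stop date, the start date will be imputed by stop date". It can only make a start earlier.

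SAP 3.7 ends the double-blind period at "the last dose of double-blind study drug if the subject continues to the OL period or" the last study visit for those who do not continue. SAP 3.8 then says: "Open-label period is defined as the time from the first dose of open-label study drug to the last study visit".

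Protocol 8.1.3 asks for a switch without a gap, and Protocol 11.8.6 gives high dose to everyone in the extension. SAP 6.4.1 lists the three sequences: High to High, Low to High and Placebo to High. The primary endpoint, the percentage of subjects with at least one TEAE, covers baseline to 12 months (Protocol 6.4).

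**The concern.** The trial has two treatment starts, and the date rules recognise only one. At the first dose the rules are cautious: a partial date in the same month or year is set to the first dosing date, so the event counts as on drug. At the switch the same rules choose the earliest day the known part allows, which is nearly always before the first open-label dose.

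An event that began on open-label high dose would then sit in the double-blind tables under the subject's randomised arm, and would be missing from the open-label tables. For a subject randomised to placebo, an event on active drug would be counted under placebo. SAP 7.1 does not correct this. Its rule for incomplete dates decides only whether an AE is treatment-emergent, not which period or treatment it belongs to. SAP 7 also sets a single Study Day 1, at the first dose of study drug.

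**Working it through.** The documents give no figure for this, so there is nothing to reproduce. The check applies the Appendix 2 start-date rules to enumerated dates.

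**Example.** First dose 20 March 2023 (placebo), first open-label dose 20 March 2024.

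- AE recorded as March 2024, day missing: imputed to 1 March 2024, before the switch.
- AE recorded as 2024, day and month missing: imputed to 1 January 2024, before the switch.
- The same rules anchored to the first open-label dose give 20 March 2024 in both cases.

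**Enumeration.** The assumptions are every first-dose date over four years (1,461 dates), a switch 365 days later, and an open-label onset on each of the next 365 days. That is 1,461 × 365 = 533,265 onsets. An AE is misdated if its imputed start falls before the first open-label dose.

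| True open-label onset | Misdated | Share |
|---|---|---|
| Day missing, switch month | 21,520 of 22,981 | 93.6% |
| Day missing, later months | 0 of 510,284 | 0% |
| Day and month missing, switch year | 266,085 of 267,545 | 99.5% |
| Day and month missing, later years | 0 of 265,720 | 0% |

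The switch-month and switch-year cases that escape are switches on the 1st of a month or on 1 January, where the imputed date equals the switch date. Moving the switch 7 days either way leaves the shares unchanged.

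**Share of all first-year open-label AEs with that kind of partial date, onset spread evenly:**

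- Day missing: 21,520 / 533,265 = 4.0%.
- Day and month missing: 266,085 / 533,265 = 49.9%.

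**Reverse direction.** With one year of first-dose dates and double-blind onset on each of 365 days (365 × 365 = 133,225), no onset is imputed on or after the switch. By period, the error runs only from open-label to double-blind.

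**Direction by arm.** Let p be the true double-blind proportion with an event, and q the chance that a subject without one gains a misdated open-label event. The observed proportion is p + (1 − p)q. All three arms take high dose in the extension. If continuation and date quality are similar across arms, q is the same in each, and the difference between arms becomes (p_high − p_placebo)(1 − q). The contrast shrinks towards zero.

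**Effect of one subject.** The plan has 8 early-stage plus 8 advanced-stage subjects per arm, so 16. One subject wrongly counted is 1/16 = 6.25 percentage points. That applies to the primary percentage only if the subject had no other double-blind TEAE, and to a preferred-term row only if the subject did not already have that term.

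**The case against.** Four points on the other side deserve weight.

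- **Assignment by imputed date is inferred.** The SAP does not say in words that AEs go to a period by imputed start date; this follows from 3.7 and 3.8. SAP 10 places derivation rules in separate documents, which could hold a period flag. This stands as a limit. Even so, Appendix 2 is the SAP's stated rule and it returns a wrong date.
- **The case is probably uncommon.** AEs are recorded continually, the diary is reviewed, missing data are queried (Protocol 11.7), and there are contacts at Months 9, 11, 12 and 15. Year-only dates should be rare. The 93.6% and 99.5% are conditional on a partial date in the switch month or year and say nothing about how often one occurs. This stands. In the other direction, the first scheduled contact after Month 12 is at Month 15, so recall is longest just after the switch.
- **A reader might infer that the error always flatters high dose.** The documents do not support that. High to High subjects are handled by the same rules, and their misdated events land in the double-blind high-dose column.
- **A reader might infer that the primary endpoint is materially distorted.** That is not shown either. A misdated event changes it only for a subject with no other double-blind TEAE, and the documents give no count of partial dates.

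Sending every ambiguous AE to open-label would also be wrong. With onset spread evenly, roughly half of the onsets in the switch month or year are truly double-blind and would be misplaced the other way.

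**Conclusion.** The point holds as a minor defect in a stated rule. A partially dated open-label AE in the switch month or year is dated before the first open-label dose in nearly all such cases (93.6% and 99.5%), and under SAP 3.7 and 3.8 it would count as double-blind. Open-label high-dose AEs are under-counted, and high-dose events are added to the placebo, low-dose and high-dose double-blind columns, diluting the comparison.

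The practical size is unknown and probably small. The conclusion assumes that AEs are allocated by imputed date, that no separate programming rule overrides Appendix 2, and, for the 4.0% and 49.9%, that onset is spread evenly over the first open-label year. The dilution also assumes similar continuation and date quality across arms.

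**What to change.** Add a rule to Appendix 2 for subjects who enter the extension. It applies when the known part of an AE start date matches that of the first open-label dose, and it allocates the AE to a period before any date is imputed:

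- Not reported by the Month 12 visit and first reported afterwards: open-label, with the start set to the first open-label dose date.
- Reported at or before the Month 12 visit, or ended before the switch: double-blind, with the existing Appendix 2 date kept.
- Undetermined: a default stated before database lock, with the double-blind TEAE table repeated with these cases allocated the other way.

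If the programming documents already hold such a rule, cite it in the SAP. The cost is one short SAP addition, minor programming on data already collected, and one extra table. Some undetermined AEs may still be placed in the wrong period; the repeated table shows whether that matters.
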